11.2.3 Response Review

The tumor imaging metrics core (TIMC) at Dana-Farber Cancer Institute or an analogous facility at collaborating sites will assess radiographic response

12. DATA REPORTING/REGULATORY REQUIREMENTS

Adverse event lists, guidelines, and instructions for AE reporting can be found in Section 7 (Adverse Events: List and Reporting Requirements).

12.1 **Data Reporting**

12.1.1 Method

The Office of Data Quality (ODQ) will collect, manage, and perform quality checks on the data for this study.

12.1.2 Responsibility for Data Submission

Investigative sites within DF/HCC or DF/PCC are responsible for submitting data and/or data forms to the Office of Data Quality in accordance with DF/HCC SOPs.

12.2 **Data Safety Monitoring**

The DF/HCC Data and Safety Monitoring Committee (DSMC) will review and monitor toxicity and accrual data from this study. The committee is composed of clinical specialists with experience in oncology and who have no direct relationship with the study. Information that raises any questions about participant safety will be addressed with the Overall PI and study team.

The DSMC will review each protocol up to four times a year or more often if required to review toxicity and accrual data. Information to be provided to the committee may include: up-to-date participant accrual; current dose level information; DLT information; all grade 2 or higher unexpected adverse events that have been reported; summary of all deaths occurring within 30 days of intervention for Phase I or II protocols; for gene therapy protocols, summary of all deaths while being treated and during active follow-up; any response information; audit results, and a summary provided by the study team. Other information (e.g. scans, laboratory values) will be provided upon request.

12.3 Multicenter Guidelines

This protocol will adhere to the policies and requirements of the DF/HCC Multi-Center Data and Safety Monitoring Plan. The specific responsibilities of the Overall PI, Coordinating Center, and Participating Institutions and the procedures for auditing are presented in Appendix C.

- The Overall PI/Coordinating Center is responsible for distributing all IND Action Letters or Safety Reports to all participating institutions for submission to their individual IRBs for action as required.
- Mechanisms will be in place to ensure quality assurance, protocol compliance, and adverse event reporting at each site.
- Except in very unusual circumstances, each participating institution will order the study agent(s) directly from supplier. A participating site may order the agent(s) only after the initial IRB approval for the site has been forwarded to the Coordinating Center.

13. STATISTICAL CONSIDERATIONS

13.1 Study Design/Endpoints

This study is an open-label phase II clinical trial. The primary endpoint is overall response rate. Secondary end points include examining the overall and complete response rates of pembrolizumab in the subgroup of patients with biologically selected subtypes of relapsed and refractory diffuse large B-cell lymphoma. We will also describe the safety and toxicity of pembrolizumab in patients with biologically selected subsets of relapsed and refractory diffuse large B-cell lymphoma. We will also report the complete response rate, duration of response, duration of complete response, progression free survival, and overall survival.

13.2 Sample Size, Accrual Rate and Study Duration

13.2.1 Sample size

The study will be powered based on the number of patients with EBV+ DLBCL enrolled. Patients with other allowed lymphoma histologies will be enrolled until the accrual goal of 20 patients with EBV+ DLBCL/TCHRLCL/plasmablastic lymphoma is met (with a maximum of 10 patients in any given lymphoma histology) at which time accrual to all lymphoma cohorts will close. The exact number of patients enrolled depends on the accrual of non-EBV+ DLBCL patients, but is expected to be 24-30 patients. If by the time 20 patients with EBV+ DLBCL are accrued, the total accrual is <24, accrual will continue to all 3 cohorts (including EBV+ DLBCL) until the total accrual reaches 24.

Six patients with histiocytic sarcoma, follicular dendritic cell sarcoma, and/or interdigitating dendritic cell sarcoma will be included in the trial and accrual to this subgroup can continue independent of closure of the study to accrual of lymphoma patients. Given the extremely rare

nature of these diseases, these patients are being included for exploratory purposes only and the statistics of the trial will not be powered based upon this patient population.

13.2.2 Statistical considerations

The hypothesis of this trial is that the response rate of pembrolizumab in this patient population will be 40% or higher. Assuming at least 20 patients are enrolled, we would consider the treatment promising if at least 6 patients respond. With this design, the study would have approximately 87% power to detect a difference in the response rate between 15% (the null hypothesis) and 40% (the alternative hypothesis), at a significance level of 0.07 (based on the exact binomial distribution). The maximal 90% confidence interval around the estimates for response and toxicity will be approximately +/-20%.

We anticipate accrual of 1 patient per month yielding an accrual period of 24 months. We anticipate following the last patient accrued for 6 months before being able to determine best overall response (the primary endpoint). Patients will be followed for 2 years after accrual for secondary endpoints such as PFS, OS, and duration of response for total study duration of approximately 4 years.

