1.2 Primary Objectives

- To examine the efficacy (overall response rate) of pembrolizumab in patients with biologically selected subsets of relapsed/refractory (R/R) biologically selected subgroups of lymphoma, using 2014 Lugano criteria (31, appendix C).

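### The single cutoff of 6 responders carries its stated 0.07 significance level and 87% power only at n=20, yet section 13.2.2 offers it for any n of at least 20 and does not say which patients count

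*Combined protocol and SAP*

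**What the plan says.** Section 13.2.2 tests a 15% null response rate against a 40% alternative. Its rule is: "Assuming at least 20 patients are enrolled, we would consider the treatment promising if at least 6 patients respond". It gives about 87% power at a significance level of 0.07 from the exact binomial distribution, and adds: "The maximal 90% confidence interval around the estimates for response and toxicity will be approximately +/-20" percent. The patients are described only as the trial's population. The same section plans one patient per month over 24 months.

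Other sections bear on who those patients are:

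- **13.2.1, group that drives power:** "The study will be powered based on the number of patients with EBV+ DLBCL enrolled". Lymphoma accrual then runs until the "accrual goal of 20 patients with EBV+ DLBCL/TCHRLCL/plasmablastic lymphoma is met", with at most 10 patients in any one lymphoma histology. I call these three histologies the core group.
- **13.2.1, total:** "The exact number of patients enrolled depends on the accrual of non-EBV+ DLBCL patients, but is expected to be 24-30 patients". If the total is below 24 when the goal is reached, "accrual will continue to all 3 cohorts (including EBV+ DLBCL) until the total accrual reaches 24".
- **13.2.1, histiocytic and dendritic cell tumours:** six patients are added, and "these patients are being included for exploratory purposes only".
- **1.2:** the primary objective is "efficacy (overall response rate) of pembrolizumab in patients with biologically selected subsets of relapsed/refractory (R/R) biologically selected subgroups of lymphoma", which is wider than the core group.
- **13.1:** response in the selected DLBCL subtypes is listed as a secondary endpoint.
- **13.7 and 13.5:** 13.7 bases the primary analysis on all enrolled patients. 13.5 restricts it to treated patients with measurable disease who were re-evaluated for response. 13.5 also requires exact 90% confidence intervals.

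**The concern.** A fixed count of responders has a known error rate only for a fixed number of patients. As n grows with the cutoff held at 6, an inactive drug reaches 6 responders more easily. The plan leaves n open above 20 and expects more than 20 patients in total, but gives no cutoff for a larger n and no statement that the extra patients are left out of the count.

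This is the only efficacy criterion in the plan. If the count were taken over all lymphoma patients, a drug at the 15% null rate would be called promising well over 7% of the time. Because the trial is open-label and the rule names no population, the choice of denominator could also be made after responses are known.

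**Working it through.** **Inputs.** From 13.2.2: cutoff r=6, null rate 0.15, alternative 0.40. The rule implies a one-sided test; the plan does not state sidedness. From 13.2.1: n=20 core patients, and a total of 24 to 30.

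**Formula.** P(X ≥ r | n, p) = 1 − Σ C(n,k) p^k (1−p)^(n−k), summed over k = 0 to r−1. Type I error uses p=0.15 and power uses p=0.40.

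**Step 1: reproduce the plan at n=20, r=6.**

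- At p=0.15 the probabilities of 0 to 5 responders are 0.0388, 0.1368, 0.2293, 0.2428, 0.1821 and 0.1028, which sum to 0.9327 before rounding. Type I error = 1 − 0.9327 = 0.0673, stated as 0.07.
- At p=0.40 the same calculation gives power 0.8744, stated as 87%.
- The widest exact (Clopper-Pearson) 90% interval at n=20 has half-width 0.198, stated as about 20 percentage points. It would be 0.181 at n=24 and 0.161 at n=30.

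All three figures are therefore n=20 figures.

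**Step 2: hold the cutoff at 6 and let n grow.**

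| n | Type I error | Power |
|---|---|---|
| 20 | 0.0673 | 0.8744 |
| 22 | 0.0999 | 0.9278 |
| 24 | 0.1394 | 0.9600 |
| 26 | 0.1850 | 0.9786 |
| 28 | 0.2354 | 0.9889 |
| 30 | 0.2894 | 0.9943 |

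Against 0.0673, the error is 0.1394/0.0673 = 2.1 times as large at n=24 and 0.2894/0.0673 = 4.3 times at n=30. Power rises, so the harm lies in false positives only. The stated accrual rate gives 1 × 24 = 24 patients, so the n=24 row is the closest to plan.

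**Step 3: apply each reading of the denominator.**

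- Exactly 20 core patients: 0.067, as stated.
- Core group including the top-up: at most n=24 and 0.139, reached only if all 24 are core patients.
- All lymphoma, with 24-30 read as lymphoma only: 0.139 to 0.289.
- All lymphoma, with the six histiocytic/dendritic patients inside the 24-30: lymphoma n is 18 to 24. If the goal of 20 core patients is met, n is 20 to 24 and the error 0.067 to 0.139.
- Evaluable patients only (13.5): the plan gives no attrition figure. Assuming 0 to 2 of 20 core patients are not re-evaluated, n is 20 to 18, the error 0.067 to 0.042 and power 0.874 to 0.791.

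**Step 4: what exactly 6 responders would show.** The upper exact 90% limit is 0.508 for 6/20, 0.435 for 6/24, 0.405 for 6/26, 0.392 for 6/27, 0.380 for 6/28 and 0.357 for 6/30. From n=27 the rule would say promising while the interval excludes the hypothesised 40%.

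**Step 5: smallest cutoff with type I error at or below 0.07.**

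| n | Cutoff | Type I error | Power |
|---|---|---|---|
| 20 | 6 | 0.067 | 0.874 |
| 21 | 7 | 0.029 | 0.800 |
| 22 | 7 | 0.037 | 0.842 |
| 24 | 7 | 0.057 | 0.904 |
| 25 | 7 | 0.070 | 0.926 |
| 26 | 8 | 0.032 | 0.878 |
| 28 | 8 | 0.049 | 0.926 |
| 30 | 8 | 0.070 | 0.957 |

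**The case against.** The strongest reply is that the rule plainly means the 20 core patients. Section 13.2.1 ties power to a named group and sets a goal of 20. Section 13.2.2 uses the same 20, and its significance level, power and interval width all fit it. A reader might see a contradiction between powering on EBV+ DLBCL and a goal of 20 across three histologies. The cap of 10 per histology argues against that: 20 literal EBV+ DLBCL patients cannot be accrued, so the term is most plausibly shorthand for the core group. This stands, and it makes the core reading credible. It does not settle the matter, because 1.2 and 13.7 point to a wider population, 13.1 makes response in the DLBCL subgroup secondary, and the top-up can take the core group itself above 20.

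A second reply is that this is an uncontrolled phase II trial whose response rates will be published with exact intervals, and that 13.3 adds results by histology. That limits the harm, since readers will see numerator and denominator. It does not fix in advance which patients the rule counts.

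Three stronger readings are tempting and not supported:

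- **That 0.07 and 87% are miscalculated.** They are right at n=20.
- **That the rule fails at larger n because the 90% interval for 6 responders then includes 15%.** So does 6/20 (0.140 to 0.508), the design point itself. Only the exclusion of 40% is specific to larger n.
- **That the six histiocytic/dendritic patients inflate the error further.** Section 13.2.1 calls them exploratory and outside the power calculation, and section 1.3 places their response rate among the secondary objectives.

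**Conclusion.** The rule is wrong as written: it lacks its stated error rate at sample sizes the plan itself allows and expects. It is not an arithmetic error at n=20. I rate it should-fix.

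The size depends on the reading. On the core reading the type I error is 0.067, rising to at most 0.139 if the top-up adds only core patients. On the all-lymphoma reading, with 24-30 taken as lymphoma patients only, it is 0.139 at n=24 and up to 0.289 at n=30. A reader might infer that the trial's true false-positive rate is about four times the stated one. The documents do not support that as a general statement: it needs both the all-lymphoma reading and the top of the expected range, whereas the planned accrual rate gives about 24 patients. The calculations assume a one-sided exact test, as the form of the rule implies.

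**What to change.** In 13.2.2, name the one population that the rule counts, and state that the six exploratory histiocytic/dendritic patients are excluded. Take all enrolled patients of that population as the denominator, in line with 13.7, and make the evaluable set of 13.5 supportive. Then choose one of two rules:

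- **(a)** Confine the rule to the first 20 core patients enrolled. The cutoff of 6, the 0.07 and the 87% all stay.
- **(b)** Tie the cutoff to the number enrolled in the named population: 6 at n=20, 7 at n=21-25, 8 at n=26-30. At n=24-30 this gives a type I error of 0.032 to 0.070 and power of 0.878 to 0.957. The cutoff should follow the number enrolled, not the number evaluable, so that patients without a re-evaluation cannot lower the bar.

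The cost is a few sentences, a short table for (b), and no extra patients. Under (a), responses in other histologies and in later core patients are reported but do not count toward the rule. Under (b), the bar rises by one or two responders, and power is 0.80 to 0.84 if only 21 or 22 patients are enrolled.

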2.1 Study Diseases

The current standard of care for patients with DLBCL who are refractory to or who relapse after first line therapy consists of salvage chemotherapy and, if a remission is achieved, consolidation by high-dose therapy with autologous stem cell transplantation (ASCT). This is typically considered the last chance at curative therapy. Unfortunately, many patients are not candidates for ASCT. Also, the majority of patients who relapse after modern first-line therapy may not achieve the remission needed to proceed to ASCT. Even among patients who do proceed to ASCT many will relapse. For patients with primary refractory disease or patients who relapse after ASCT, the outcomes are dismal. Thus, relapsed/refractory DLBCL represents an urgent, unmet clinical need.

Immune checkpoint blockade is a promising strategy in DLBCL. Immune checkpoint blockade has already established a favorable track record in the treatment of DLBCL. The anti-PD1 antibody pidilizumab administered to patients with DLBCL after ASCT proved to be safe and associated with promising response rate and progression-free survival especially among the higher risk subgroup of patients on the trial¹. In a phase 1b study of patients with hematologic malignancies, another anti-PD1 antibody, nivolumab, was associated with a response rate of 36% in DLBCL².

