It is possible to select a subset of DLBCL tumors which may be particularly vulnerable to PD-1 blockade. In two independent phase 1 studies of PD-1 blockade (one using the monoclonal antibody nivolumab and one using pembrolizumab), patients with heavily pre-treated relapsed/refractory classical Hodgkin lymphoma had remarkably high response rates (87% and 65%, respectively)^{3,4}. This validated the pre-clinical work showing that HL tumor cells very frequently over-express the PD-1 ligands PD-L1 and PD-L2 on the cell surface, most often as a result of genetic amplification events at the 9p24.1 locus⁵. These results lend credence to the hypothesis that some hematologic malignancies such as HL may have particularly strong dependence on the PD-1 pathway for survival, and that those tumors are ideal targets for PD-1 blockade. In the case of DLBCL, PD-L1 expression on the tumor cell surface, while encountered occasionally, is not a universal event, and that genetic events such as occur in HL are rare. This difference may explain the variation in response rates between the two histologies seen in clinical studies. It also suggests that selecting DLBCL subtypes with a dependence on PD-1 could result in significantly higher response rates.

Recent work has demonstrated that there are indeed subtypes of DLBCL that seem to have a high frequency of PD-L1 surface over expression, implying a larger reliance on checkpoint blockade for survival and a higher vulnerability to PD-1 blockade. One of those subtypes is primary mediastinal B-cell lymphoma (PMBL), which like HL frequently harbors genetic amplification at 9p24^{6,7}. The susceptibility of this entity to pembrolizumab is being tested in an ongoing phase II trial. The other DLBCL subtypes with frequent PD-L1 over expression are EBV-positive DLBCL, post-transplant lymphoproliferative disease (PTLD), plasmablastic lymphoma, and the histological variant of DLBCL T-cell/histiocyte rich DLBCL (TCRLBCL)^{8,9}. These DLBCL subtypes represent 30% of unselected DLBCLs.

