2.3 Rationale

It is possible to select a subset of lymphomas as well as histiocyte/dendritic cell neoplasms that frequently over-expresses PD-L1 or, in the case of AITL, are characterized by near universal PD-1 expression. Such selection could significantly increase the response rate to PD-1 blockade compared to that of an unselected population. If the hypothesis is confirmed, it could define a subset of patients in whom pembrolizumab is a therapeutically useful agent. We therefore propose a multicenter phase 2 trial of pembrolizumab in patients with biologically selected subtypes of lymphoma and histiocyte/dendritic cell neoplasms. The goal of this study is to lay the groundwork for a new treatment paradigm in this lymphoma subgroup.

The choice of the 200 mg Q3W as an appropriate dose for is based on simulations performed using the population PK model of pembrolizumab showing that the fixed dose of 200 mg every 3 weeks will provide exposures that 1) are optimally consistent with those obtained with the 2 mg/kg dose

every 3 weeks, 2) will maintain individual patient exposures in the exposure range established in melanoma as associated with maximal efficacy response and 3) will maintain individual patients exposure in the exposure range established in melanoma that are well tolerated and safe.

A fixed dose regimen will simplify the dosing regimen to be more convenient for physicians and to reduce potential for dosing errors. A fixed dosing scheme will also reduce complexity in the logistical chain at treatment facilities and reduce wastage.

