3. PARTICIPANT SELECTION

3.1 Eligibility Criteria

- 3.1.1 Be willing and able to provide written informed consent for the trial.
- 3.1.2 Histologically confirmed diagnosis of a histiocyte/dendritic cell neoplasm or relapsed/refractory aggressive lymphoma with at least one of the following features (with review required at a participating study center):
 - Diffuse large B-cell lymphoma with EBV positive tumor cells (defined as positive EBV-encoded RNA in tumor cells)
 - Diffuse large B-cell lymphoma, leg type (DLBCL-LT)
 - Plasmablastic lymphoma
 - T cell/histiocyte rich DLBCL
 - EBV+ T cell lymphoma of any histology; note, patients with angioimmunoblastic T cell lymphoma will be eligible regardless of EBV status
 - Histiocytic sarcoma
 - Follicular dendritic cell sarcoma
 - Interdigitating dendritic cell sarcoma
- 3.1.3 For patients with histiocytic sarcoma, interdigitating dendritic cell sarcoma, or follicular dendritic cell sarcoma only: disease that is not amenable to surgical resection and/or radiation therapy with curative intent.

- 3.1.4 For lymphoma patients only: At least one prior systemic chemotherapy including an alkylating agent and anthracycline (unless contraindicated), and an anti-CD20 monoclonal antibody if the tumor is CD20+. Prior treatment with anthracycline and alkylating agent is not required for patients with NK/T cell lymphoma but prior treatment with platinum-based chemotherapy and/or l-asparaginase is required.
- 3.1.5 For lymphoma patients only: Participants must have received and relapsed after autologous stem cell transplantation (ASCT), or be ineligible for ASCT (including on the basis of refractory disease), or have declined ASCT
- 3.1.6 Age 18 years or older at the time of signing consent.
- 3.1.7 ECOG performance status of 0 or 1 (Karnofsky $\geq 70\%$, see Appendix A)
- 3.1.8 Participants must have normal organ and marrow function as defined below:
 - absolute neutrophil count $\geq 500/\text{mcL}$
 - platelets $\geq 75,000/\text{mcL}$ ($\geq 30,000$ if there is bone marrow involvement with lymphoma)
 - total bilirubin ≤ 1.5 times the institutional upper limit of normal (ULN) OR direct bilirubin \leq the normal in subjects with total bilirubin >1.5 times the ULN
 - AST(SGOT)/ALT(SGPT) $\leq 2.5 \times$ institutional ULN or ≤ 5 times ULN in patients with known hepatic involvement with lymphoma
 - albumin $\geq 2.5 \text{ mg/dL}$

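### Does the 6-of-20 rule against a 15% null need a stated limit, given that the rationale is that selection raises response?

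*Combined protocol and SAP*

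**What the plan says.** The scientific case is in sections 2.1 and 2.3. Section 2.1 reports that "nivolumab, was associated with a response rate of 36% in DLBCL" and suggests that "selecting DLBCL subtypes with a dependence on PD-1 could result in significantly higher response rates". Section 2.3 extends this to the whole study population: "Such selection could significantly increase the response rate to PD-1 blockade compared to that of an unselected population". It continues: "If the hypothesis is confirmed, it could define a subset of patients in whom pembrolizumab is a therapeutically useful agent".

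The formal rule is in section 13.2.2. That section opens by putting the trial's hypothesis as a pembrolizumab response rate of at least 40% in the population studied. With at least 20 patients, "we would consider the treatment promising if at least 6 patients respond". The design is credited with "approximately 87% power to detect a difference in the response rate between 15% (the null hypothesis) and 40% (the alternative hypothesis". Its type I error is put at 0.07, worked out from exact binomial tails. No source is given for 15%, there or elsewhere.

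The study is single-arm (section 1.1), and the primary objective is to examine the overall response rate (section 1.2). Eligibility goes beyond DLBCL and includes "EBV+ T cell lymphoma of any histology" (section 3.1). Section 13.1 adds: "Secondary end points include examining the overall and complete response rates of pembrolizumab in the subgroup of patients" with selected DLBCL subtypes. Response rates are to be reported with exact 90% confidence intervals (sections 13.5 and 13.6).

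**The concern.** The word hypothesis seems to carry two meanings. In section 2.3 it follows directly on the claim that selected patients respond better than unselected ones. In section 13.2.2 it is an absolute response rate. A reader who joins the two could take 6 responders in 20 as confirmation that selection works.

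The numbers make that reading tempting and unsafe. The bar of 6/20 is 30%, which lies below the cited 36%, and the 40% alternative is only 4 points above it. If 36% were what unselected patients achieve, a treatment that gained nothing from selection would usually pass. At stake is an overstated conclusion, that pembrolizumab response depends on biological selection, drawn from a test that shows only activity above an unsourced floor.

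**Working it through.** **Inputs.** From section 13.2.2: n = 20, success if X ≥ 6, null 15%, alternative 40%. From section 2.1: 36% for nivolumab in DLBCL. From section 13.5: exact 90% intervals. Assumed, because the documents give no firm unselected rate: 20%, 25% and 30%.

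**Step 1: the plan's own figures.** The success probability at true rate p is the sum over k = 6 to 20 of C(20,k) p^k (1−p)^(20−k).

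- p = 0.15: 1 − P(X ≤ 5) = 1 − 0.9327 = 0.0673, which is 0.07 to two decimals.
- p = 0.40: 1 − 0.1256 = 0.8744, the stated 87%.

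Both figures reproduce.

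**Step 2: the same rule at other true rates.**

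| True response rate | P(at least 6 of 20) |
|---|---|
| 15% (null) | 0.067 |
| 20% (assumed) | 0.196 |
| 25% (assumed) | 0.383 |
| 30% (assumed) | 0.584 |
| 36% (cited, nivolumab) | 0.783 |
| 40% (alternative) | 0.874 |

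Between 36% and 40% the success probability differs by 0.874 − 0.783 = 0.091. The rule does not separate those two rates.

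**Step 3: intervals at and above the bar.** The Clopper-Pearson 90% limits are:

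- 6/20: 14.0% to 50.8%
- 11/20: 34.7% to 74.1%
- 12/20: 39.4% to 78.3%

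The lower limit first passes 36% at 12 responders. At a true rate of 40%, P(6 ≤ X ≤ 11) = 0.8744 − 0.0565 = 0.818. Most expected successes would therefore have an interval that still contains 36%. The 6/20 interval also contains 15%, because a two-sided 90% interval leaves 5% in each tail while the rule's exact type I error is 6.7%. That has no bearing on selection.

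**Step 4: what a test of enrichment would take.** Put the null at 36% and keep n = 20 with one-sided error of at most 0.07. The bar becomes 11 responders (error 0.0645) and power at 40% is 0.128. Separating 36% from 40% at error 0.07 and power 0.87 needs about 1,000 patients. The limitation comes from the trial's size and single arm, and wording cannot remove it.

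**Step 5: does the plan claim more than activity?** Section 13.2.2 states its hypothesis as an absolute rate and attaches only the word promising to a pass. The summary that closes section 2.1 offers, as the testable hypothesis, that these tumours are a promising target for anti-PD-1 treatment, and names further study as the consequence. Section 2.3 is looser, but its consequence is conditional and concerns whether the drug is useful in these patients. No section sets a rule under which 6/20 establishes a gain over unselected patients.

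**The case for a change.** The strongest case for a change is that the protocol presents this trial as a test of its rationale and twice says what follows if the hypothesis is confirmed. The limits of a positive result are best fixed before data are seen, and a line or two would cost no patients. The worry also does not depend on 36% being the right benchmark: with an unselected rate of 30% and no gain from selection, the rule would still pass with probability 0.584. And 15% determines both the type I error and the bar, so its basis is a fair thing to ask for.

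Two parts of this stand. The basis for 15% is not written down, and section 2.3 uses hypothesis more loosely than section 13.2.2. Neither affects the analysis. An activity floor does not have to equal the response rate of an unselected population, and a disclaimer about what a single-arm test cannot show leaves the sample size, bar, endpoint and intervals as they are.

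The further idea, reporting the DLBCL-subtype rate beside 36%, is a doubtful trade. That figure comes from a different antibody in a phase 1b study and has no denominator in the documents. Section 2.1 puts the targeted subtypes at 30% of unselected DLBCL, so the cited cohort may already include some of them. Setting the two rates together invites the very inference to be avoided, and the planned subgroup rates with exact intervals already let readers judge precision.

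**Conclusion.** No change is needed. Followed as written, the plan gives a sound activity conclusion: at n = 20, 6 or more responders has probability 0.067 if the true rate is 15% and 0.874 if it is 40%, as stated. The design cannot show that selection raises response (0.783 chance of passing at 36%), but section 13.2.2 does not say that it does. The missing basis for 15% and the loose wording in section 2.3 are matters of explanation that careful analysts will handle in the report by describing a pass as activity above 15%.

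This rests on two conditions. The 36% is used only as an illustrative rate and the 20% to 30% range is assumed. All figures are for exactly 20 patients; how the bar of 6 would apply at the 24 to 30 patients expected in section 13.2.1 is a separate question and is not judged here.
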